10.4. STUDY INTERVENTION(S) ADMINISTRATION: EVIDENCE-BASED EXERCISE AND MANUAL THERAPY

Evidence-Based Exercise and Manual Therapy (EBEM) is provided by a licensed physical therapist or Doctor of Chiropractic. Evidence-based guidelines, including those from the American College of Physicians, the Agency for Healthcare Research and Quality, and the Departments of Defense and Veterans' Affairs, indicate that exercise and manual therapy are beneficial for persons with chronic back pain. Practice Guidelines and Systematic Reviews support benefits of exercise and manual therapy for persons with chronic LBP. ^{59,60}

Exercise and manual therapy interventions are most commonly provided to persons with LBP by physical therapists and Doctors of Chiropractic. Exercise helps patients with chronic LBP recover and avoid recurrence. Exercise has positive impact on both mental and physical well-being and will be included in every EBEM session. Evidence-based guidance is provided to direct decision-making on tailoring the particular type of exercise that is best-suited to each individual study participant.

Although systematic reviews have not found any specific type of manual therapy or exercise superior to another for all patients with LBP, there is support for decision-making strategies that describe how exercise and manual therapy interventions should be personalized to individual patients with LBP.

Evidence supports a multimodal approach combining exercise with manual therapy. Manual therapy is therefore included in each EBEM session. Evidence-based guidance is provided to direct decision-making on the particular type of manual therapy that may be best suited to an individual study participant. Special attention is paid to the clinician's choice of language in regard to the purpose and expected outcomes of manual therapy in order to avoid enhancing catastrophizing ideations or preference for passive interventions.

The EBEM intervention will train licensed physical therapists and Doctors of Chiropractic to personalize care to individual participants and enhance their effectiveness. These strategies are outlined below:

Risk Stratification

Risk stratification involves identifying physical and psychological factors associated with developing prolonged disability and providing treatments to address the specific risk factors present in an individual patient. The type and dosage of the EBEM treatment components (exercise, manual therapy and education) will be based on the participant's degree of risk. Training will provide guidance on how each of the treatment components can be tailored to participant's risk based on the results of the STarT Back Screening Tool collected at the baseline visit.

Intervention Tailoring

The core components of EBEM (exercise and manual therapy) will be tailored to address the unique needs of an individual participant. Training will focus on Treatment-Based Classification (TBC) as a decision-making framework with evidence to support its effectiveness. The TBC decision-making framework trains clinicians to tailor the particular selection of exercise and manual therapy techniques to individual patients with back pain.

Education Strategies

All participants will be helped to understand the biopsychosocial model of pain, which places emphasis on the important role of thoughts and attitudes as well as environmental factors on the pain experience. Key messages include the importance of remaining active and maintaining a positive outlook towards recovery. Education strategies are also designed to enhance participants' self-efficacy through motivation-enhancing communication and shared-goal setting procedures. Training will emphasize recommended communication strategies for establishing an optimal supportive and collaborative relationship with participants.

10.4.1.DOSING AND ADMINISTRATION

The EBEM intervention will be provided in face-to-face, one-on-one, sessions with a licensed physical therapist or Doctor of Chiropractic who has been trained in the intervention protocol. A total of 10 sessions will be provided over an 8-week treatment period. Two sessions per week are provided in the first two weeks followed by weekly sessions over the next 6 weeks. If visits are missed and/or need to be rescheduled, visits may be scheduled for up to 12 weeks. No more than 10 visits will be scheduled for participants newly randomized to EBEM in either the first or second intervention period. For participants maintaining EBEM in the second treatment period, no more than 4 visits will be scheduled. Treatment sessions will last approximately 60 minutes each.

Providers will be licensed PTs or DCs with at least 1 year experience working with patients with cLBP. Providers are required to attend 12 hours of training covering performance of specific techniques, adaptations to telehealth, risk stratification, tailoring, and participant education procedures. Some training content will be online.

Study providers will have their intervention visits monitored for fidelity via a video recording or inperson observation once they are certified to deliver the intervention. Fidelity assessments will be conducted with greater frequency during the early stages of enrollment and then as needed. Video recordings/observations will be reviewed/performed by investigators or designee and evaluated for the criteria on a fidelity checklist. Fidelity assessments will focus on verifying that the exercise and manual therapy components were delivered as outlined in the protocol, and that no prohibited interventions were delivered. Individual providers will receive additional or remedial training in the intervention protocol whenever deficiencies in fidelity are observed.

EBEM Protocol for Second Randomization Period

Participants randomized to continue receiving EBEM in the second period intervention will receive 4 additional in-person EBEM sessions during weeks 1-4 of this period. If visits are missed and/or need to be rescheduled, visits may be scheduled up to 5 weeks from the date of the first augmenting/maintenance visit.

10.4.2. ACQUISITION AND ACCOUNTABILITY

Licensed Doctors of Chiropractic and physical therapists are eligible to be trained in the EBEM study protocol. Training will consist of a total of 12 hours of content covering the performance of specific exercise and manual therapy techniques as well as instruction in procedures for risk stratification, intervention tailoring using the TBC decision-making framework, and communication and motivation.

10.4.3. STUDY INTERVENTION COMPLIANCE

Adherence to the intervention will be assessed in terms of attendance to in-person sessions. Compliance with the first period EBEM treatment is defined as completion of at least 8 of the 10 prescribed visits. Compliance with the second period EBEM treatment is defined as completion of at least 3 of the 4 prescribed visits

10.4.4. MEASURES TO MINIMIZE BIAS: RANDOMIZATION AND BLINDING

The **first-stage randomization** will use a randomized version⁶¹ of the Minimization method^{62,63} to maintain marginal covariate balance. Minimization is an alternative to stratified permuted block randomization for maintaining (marginal) covariate balance across treatments that is better equipped to handle a larger number of factors to balance on. When a participant is randomized, a measure of the marginal discrepancy between treatments is calculated and the patient is randomized using a biased coin method where whichever treatment would make the discrepancy smallest has a higher probability and the other treatments have equal, smaller probabilities. Covariates included in minimization algorithm:

[figure not shown]
- Willingness to participate in deep phenotyping (yes/no)
- Depressive or anxiety symptoms (yes/no)
- Duration of pain symptoms (<5 years/≥5 years)
- Current use of opioid treatment (yes/no)

A total of approximately 740 participants will be randomized to ACT (n=185), duloxetine (n=185), ESC (n=185), and EBEM (n=185) and which will require recruitment of approximately 820 participants, anticipating that 10% will not be randomized due to failure to meet eligibility criteria at the end of the run-in phase and an estimated 15% will be lost to follow-up over the course of the study. Participants who did not complete required run-in procedures will not be randomized. In order to assign equal numbers of participants to each of the 4 study interventions, randomization probabilities will account

for the fact that certain participants, e.g., because of a contraindication, may be eligible for only 3 of the 4 treatments.

Second-stage randomization will occur at the end of the first treatment period. Response to treatment will be assessed using the PEG and PGIC. Based on these scores, individuals will be grouped into 4 response classes.

- Group 1 participants (PGIC 1-2 and PEG <4) are assigned to maintain the first-line treatment.
- Group 2 participants (PGIC 1-2, PEG ≥4) are assigned to maintain the current treatment and augment with a randomly selected additional treatment.
- Group 3 participants (PGIC 3-4) are randomized to an **augmentation treatment or to switch** to a new treatment.
- Group 4 participants (PGIC 5-7) are randomly assigned to switch to a second-line treatment.

^{*} Patients initially randomized to ESC with 12-week PGIC scores of 3-7 will be randomized to augmentation and not switching.

Table 10.1 provides a list of all possible augmentations (combinations of the initial treatment with a second study intervention) and treatment switches for each of the initial treatment assignments. This randomization will be performed within initial treatment by using the minimization method^{62,63} to achieve study-wide balance across treatments. Over the course of the study, the number and proportion of participants assigned to augmentation and switching overall, blinded to initial treatment assignment, will be monitored. If the proportions in each group differ meaningfully from the underlying assumptions used in the estimation of sample size, the proportion randomized to augment vs switch within Group 3 will be adapted to maintain power.

All Potential Second Stage All Potential Sw		All Potential Switches to Second
First Stage Treatment	Augmentations	Treatments
ESC	ESC + ACT	N/A
	ESC + Duloxetine	
	ESC + EBEM	
ACT	ESC + ACT	ESC
	ACT + Duloxetine	Duloxetine
	ACT + EBEM	EBEM
Duloxetine	ESC + Duloxetine	ESC
	ACT + Duloxetine	ACT

	Duloxetine + EBEM	EBEM
EBEM	ESC + EBEM	ESC
	ACT + EBEM	ACT
	Duloxetine + EBEM	Duloxetine

Participants who must discontinue first-stage treatment early, regardless of their PGIC or PEG score, will be randomized to switch to a second treatment. These individuals will discontinue treatment and will be randomized to switch to a second-line treatment 12 weeks post baseline (Visit 1).

Randomization will be performed using the Carolina Data Acquisition and Reporting Tool (CDART), developed by the Collaborative Studies Coordinating Center at the University of North Carolina. CDART is designed and implemented as a centrally hosted, web-based, customizable and scalable data management system. Randomization algorithms will be developed by a biostatistician and custom-written in Java, which provides a full set of libraries and tools capable of complex algorithm implementation. This data management system will provide a means for implementing treatment allocation protocols, masking allocation of future participants, and for study staff to obtain allocation information immediately following randomization. Study staff and participants will not be blinded to treatment allocation given the nature of the interventions. Study investigators and staff involved in data analysis will be blinded to assignment.

Although patients and providers cannot be blinded with respect to study interventions, during the study data summaries produced for review by the study team that involve primary and secondary endpoint data will be blinded (e.g., treatment groups randomly permuted). Unblinded summaries may be required for review by the DSMB. Study team members involved in producing DSMB reports and/or presenting unblinded data to the DSMB will have no role in development of the study's statistical analysis plan.

11. STUDY INTERVENTION DISCONTINUATION AND PARTICIPANT DISCONTINUATION/WITHDRAWAL

11.1. DISCONTINUATION OF STUDY INTERVENTION

Early discontinuation of treatment is anticipated to be rare. Examples include a broken leg, precluding continuation of EBEM, or adverse reaction to duloxetine, necessitating discontinuation of duloxetine treatment.

11.2. PARTICIPANT DISCONTINUATION/WITHDRAWAL FROM THE STUDY

A participant may be discontinued from the study if he/she is shown to not meet the inclusion criteria based on new information that was not available at the time of initial enrollment and continuing in the study poses a safety risk (e.g., pregnancy or development of liver failure if on duloxetine). Participants should not be discontinued for reasons other than new information that constitutes a safety risk. For example, if new information indicates that a participant meets one of the exclusion criteria for an intervention, but the criteria does not pose a safety risk to the participant, then the participant should not be discontinued. In this case, the participant will be considered in violation of the protocol for that

period and excluded from the per protocol analysis (see Sections 10.1.4, 10.2.4, 10.3.4, and 10.4.4). In general, participants with poor compliance but at no increased risk will continue in the study to complete all study assessments and minimize attrition.

Other criteria for participant discontinuation at any point in the study:

- Participant meets one or more of the safety exclusion criteria defined in Section 8.
- Study physician determines that continuation in the study is not in the best interest of the participant.
- Participants can withdraw consent from the protocol at any point, and that will lead to
 discontinuation from the study. At that point, the investigator will make reasonable effort to
 ensure participant's well-being and safety and provide a termination visit with appropriate
 documentation.
- The site investigator may decide to stop a participant's treatment due to side effects or other safety concerns for the participant and/or site staff. If the participant is participating in the duloxetine intervention arm at the time of discontinuation from the entire study, the participant will be advised to taper their dose as outlined in Section 10.2. or obtain a prescription for duloxetine from their primary care physician or other provider.

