Participants may need to discontinue treatments prior to the end of the 12-week treatment period (e.g., following an adverse reaction to duloxetine; see Section 10.2.1 for list of reasons). Participants needing to discontinue first period treatment will be switched to a randomly selected second treatment at Visit 1. Participants needing to discontinue second period treatment will remain in the study and undergo all future assessments for which they are eligible.

The study will enroll approximately 820 participants in order to randomize approximately 740 individuals and to have approximately 630 completers (i.e., 15% dropout rate after randomization assumed). Assuming dropout occurs uniformly across study interventions, the sample size of 740 randomized will result in having approximately 80% probability of estimating a DTR within 90% of the optimal DTR based on the study's primary endpoint. See Section 13.2 for additional details on sample size needs for precision medicine objectives, including assumptions regarding intervention effect sizes.

The interventions under evaluation are evidence-based, with established efficacy and are standard of care. Therefore, we do not expect they will pose safety risks such that these interventions need to be stopped before the end of the study. Safety data and adverse events will be monitored. These data will be reported to and reviewed by a Data Safety and Monitoring Board. Generally, this trial will inform a precision medicine approach to the treatment of chronic low-back pain and therefore we are not planning interim analyses for futility or efficacy in order to maintain sufficient power for the precision medicine analyses. Blinding is not feasible for study participants or staff involved in the delivery of interventions. Investigators involved in the analysis of study data will be blinded to treatment assignment.

The study timeline involves approximately 9 months of participant enrollment across 12 sites for a total of 820 enrolled. Sites will enroll ~7 participants per month. We anticipate that ~90% of participants who consent at the Enrollment Visit will be randomized at the end of the 2-week run-in at Visit 0 and that 85% of randomized participants will complete all study activities. The total study duration for all participants is 38 weeks. To minimize participant burden, where possible, data will be collected remotely.

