7.4. END OF STUDY DEFINITION

For study non-completers, the end of the study will coincide with the point in time when the participant notifies study personnel that they wish to discontinue the study. If the reason for study discontinuation is related to an incidence adverse event, and if the participant consents to further contact by study staff, the participant will be contacted by phone 4 weeks after completion of the study discontinuation visit to follow up on adverse events and document their resolution or status.

The study will end approximately 38 weeks after randomization (at the time of completion of the 12-week post-intervention follow-up period).

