12.2. SAFETY ASSESSMENTS

Participants will be screened for contraindications to any of the BEST study interventions and phenotyping procedures prior to enrolling in the study. At the baseline visit, participant medical history will be obtained by the clinical coordinator and a physical assessment will be performed by a qualified medical professional. Basic safety assessments will be performed at 6 weeks (midpoint of intervention period one), 12 weeks (Visit 1), 18 weeks (midpoint of intervention period two), 24 weeks (Visit 2), and 36 weeks post-baseline (12 weeks after intervention period two) to assess participant tolerability to their current study intervention(s). Patients who are unable to tolerate their assigned study treatment will be educated on how to safely discontinue their current treatment plan but will otherwise remain in the study. Study staff will conduct an additional assessment of participants randomized to duloxetine via phone on day 7 (or next business day if falls on a weekend) of the intervention phase with participants newly randomized to duloxetine (i.e., day 7 of either the first or second intervention period).

Participants will be asked to report pregnancy status at multiple time points: prior to enrollment at Prescreening and Screening, and prior to randomization at the Baseline and 12-Week visits. Participants who report pregnancy prior to randomization to the first period intervention are excluded from the study. If the participant becomes pregnant during the study, duloxetine will be rapidly tapered. Participants who become pregnant during the study will not undergo study MRIs.

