We expect missing data to be minimal because of study procedures discussed previously to enhance retention such as incentives, incorporation of patient stakeholder feedback in the development of study materials, and efforts to minimize participant burden. In addition, there will be ongoing participant engagement through a study website, contact with research staff and regular patient engagement efforts. Finally, protocols for discontinuation of study treatment that are not tolerated are planned to enhance retention. We will continue to follow all participants until the end of the study and will utilize alternative forms of data collection for those who do not attend planned study visits (e.g., telephone administration or online data collection). Despite these efforts, missing data will arise and, as needed and appropriate, will be addressed using non-parametric multiple imputation procedures. Sensitivity analyses will be presented in detail as part of the SAP.

13.4.2.ANALYSIS OF THE PRIMARY EFFICACY ENDPOINT(S)

Complete details will be provided in the formal Statistical Analysis Plan for the study.

13.4.3.ANALYSIS OF THE SECONDARY ENDPOINT(S)

Complete details will be provided in the formal Statistical Analysis Plan for the study.

13.4.4.SAFETY ANALYSES

No safety analyses are planned other than descriptive summaries and data listings of reported adverse events.

13.4.5.BASELINE DESCRIPTIVE STATISTICS

Complete details will be provided in the formal Statistical Analysis Plan for the study.

13.4.6.PLANNED INTERIM ANALYSES

No interim analyses are planned for the study. Adaptation to the design, *i.e.* the second stage randomization probabilities, is planned and details will be included in a future Statistical Analysis Plan. Briefly, overall proportions of participants assigned to augment or switch will be monitored. If proportions deviate meaningfully from assumptions, we will consider shifting randomization probabilities within Group 3 (*e.g.*, from 50/50 to 60/40 augment/switch).

13.4.7.SUB-GROUP ANALYSES

N/A

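### Section 11.2 permits study exit when treatment is stopped for side effects or a safety criterion is met, while the rest of the protocol keeps such participants under follow-up, so Week 24 PEG could be lost for tolerability reasons

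*Protocol*

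**What the plan says.** Protocol Section 11.2 deals with leaving the study. Its opening allows this when new facts show that a participant does not meet the entry criteria and that continuing would be unsafe; pregnancy, and liver failure on duloxetine, are its examples. It then says nobody should be discontinued on any other ground. A list follows under "Other criteria for participant discontinuation at any point in the study". Two of its entries are "Participant meets one or more of the safety exclusion criteria defined in Section 8" and "The site investigator may decide to stop a participant's treatment due to side effects or other safety concerns for the participant and/or site staff". The second entry goes on to give taper advice for someone on duloxetine who is leaving the study altogether.

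Other sections treat intolerance as the end of an intervention only. Sections 4.1 and 12.2 keep such participants enrolled. Under 5.2.3, 7.1, 10.2.1 and 10.4.4, those who stop in the first period are randomized to something else at Visit 1. For the second period, 7.1 says: "Participants needing to discontinue second period treatment will remain in the study and undergo all future assessments for which they are eligible". On pregnancy, 12.2 says: "Participants who become pregnant during the study will not undergo study MRIs". On follow-up, 13.4.1 says: "We will continue to follow all participants until the end of the study".

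The SAP (Missing Data) assumes missing at random and includes every randomized participant. It contains no sensitivity analysis, although Protocol 13.4.1 said that sensitivity analyses would be presented in the SAP.

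**The concern.** A site with a participant whose treatment has been stopped for side effects finds two instructions. One keeps the participant in, with a second randomization or all later assessments. The other lists the same event among the reasons for leaving the study. If a site follows the second, the Week 24 PEG is not collected, and for a first-period stop the second-stage randomization is lost as well. The reason for the loss would be tolerability or safety, which may be related to outcome and may occur more often in one arm than in another.

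The loss would also be avoidable. The outcomes are self-reports on a web platform (12.1), and 13.4.1 already plans telephone or online collection for people who do not attend visits.

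**Working it through.** **1. Text against text.** For intolerance, Sections 4.1, 5.2.3, 7.1, 10.2.1, 10.4.4 and 12.2 agree: the treatment stops and the participant stays. The side-effect entry in 11.2 names stopping treatment as the act, says the investigator may do it, and places it among reasons to leave the study. For the Section 8 entry, the direct conflict is with 13.4.1, since the other sections mainly address intolerance or the need to stop a treatment. For pregnancy there is a further conflict with 12.2, whose MRI sentence only has a use if the participant is still enrolled. Within 11.2, the list is wider than the opening limit: it adds the study physician's view of best interest and staff safety.

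Section 11.2 also shows other signs of not having been reconciled. It relies on a per-protocol analysis that is not among the populations in 13.3. Its cross-references lead to drug storage (10.2.4), to randomization (10.4.4) and to a Section 10.3.4 that does not appear.

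**2. The plan's own dropout arithmetic.** Inputs: 630 completers and 15% dropout (13.2), and 10% run-in loss (4.1).
- Randomized: 630 / (1 - 0.15) = 741.2, rounded up to 742; the plan says about 740.
- Enrolled: 740 / (1 - 0.10) = 822.2, rounded up to 823; the plan says about 820.

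Both figures reproduce and neither is in dispute.

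**3. Illustrative size.** The documents give no rate of removal under 11.2, so f and D below are assumptions. Let a share f of an arm be removed, and let their mean Week 24 PEG change be D SD worse than that of the rest, whose mean is m. The full-arm mean is (1 - f)m + f(m - D) = m - fD, and the complete-case mean is m. The shift is therefore f x D. The last column assumes, in addition, that removals come on top of the 15% dropout: 740 x (1 - 0.15 - f).

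| f | D = 0.3 | D = 0.5 | D = 1.0 | Completers |
|---|---|---|---|---|
| 2% | 0.006 | 0.010 | 0.020 | 614 |
| 5% | 0.015 | 0.025 | 0.050 | 592 |
| 10% | 0.030 | 0.050 | 0.100 | 555 |

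**4. Yardstick.** Section 13.2 assumes standardized effects of 0.25 (ACT), 0.3 (duloxetine) and 0.4 (EBEM). The gaps are 0.3 - 0.25 = 0.05, 0.4 - 0.3 = 0.10 and 0.4 - 0.25 = 0.15 SD. At 2% the shift is small beside these. At 5-10% in a single arm, with D toward the upper end, it reaches the size of the smaller gaps.

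**5. Actual counts.** The SAP reports 805 randomized to Stage 1 and 683 to Stage 2: 805 - 683 = 122, or 122 / 805 = 15.2%. No reasons are given.

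**The case against.** The strongest reply is that Section 11.2 does not remove anyone. The side-effect entry is permissive and names stopping treatment; the sentence about leaving altogether can be read as taper advice for those who also happen to leave. Section 11.1, directly before it, uses an adverse reaction to duloxetine as an example of stopping an intervention and expects such stops to be rare. Several sections state the opposite rule plainly, and nothing shows that any site applied 11.2 as study exit. A permission to discontinue a pregnant participant can coexist with a default for those who are not discontinued. Section 7.4, where "the end of the study will coincide with the point in time when the participant notifies study personnel that they wish to discontinue", describes ordinary voluntary withdrawal and is not a contradiction.

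On size, f x D is a complete-case figure. The SAP fits a mixed model to all randomized participants and uses whatever PEG values precede exit, and the protocol plans multiple imputation where needed. The SAP also places the regime estimate outside its scope.

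Most of this stands, and it limits the point to an unresolved permission. It does not remove it: a heading about leaving the study, with these entries beneath it, can be followed in good faith. The mixed model's covariates are the minimization variables, week and the number of eligible treatments; tolerability is not among them.

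A reader might go further and infer that duloxetine is made to look better, for instance by assuming that 10-15% of its 198 participants (20-30 people) were removed. The documents do not support that rate; at 2% it would be about 4 people (198 x 0.02). Nor do they support the direction: first-period stoppers kept in the study would have received a different second treatment, and nothing says how they would have scored at Week 24.

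**Conclusion.** The inconsistency is real and should be corrected. Section 11.2 permits, without mandating, study exit on grounds that other sections treat as stopping an intervention, and it conflicts with its own opening limit, with 13.4.1 and, for pregnancy, with 12.2.

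The consequence is conditional. It requires sites to have used 11.2 as study exit and missing at random to fail for those who left. The illustrated shift is negligible to small if removal is rare, as 11.1 expects, and comparable with the assumed gaps between treatments only at about 5-10% concentrated in one arm. Those gaps are single-treatment effects from the simulation, so they serve only as a rough yardstick for Stage 1 arm means at Week 24.

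The 122 participants not randomized to Stage 2 should not be read as evidence of removals under 11.2. Nor should hypothetical removals simply be added to them, since any first-period removals would already be among the 122.

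**What to change.** Reconcile Section 11.2 with 4.1, 7.1, 12.2 and 13.4.1 by separating two things: stopping an intervention, and stopping outcome collection. State that anyone whose treatment or in-person participation is stopped still receives the remote PEG, PGIC and secondary questionnaires unless they withdraw consent to further contact. The clinical grounds themselves (pregnancy, liver failure, the study physician's judgment, staff safety) are for the sponsor to reconcile across the sections; this change to data collection does not depend on how that is settled.

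Because the SAP already reports 805 and 683 randomized, rewording alone may come too late to recover outcomes. Two additions to the analysis are therefore needed:
- Report by Stage 1 arm how many exits were investigator-initiated, how many were consent withdrawals and how many were losses to follow-up. The Appendix 1 flow table already has rows for reasons of non-completion. Its columns for a treatment alone pool strong responders with people not assessed at the end of Stage 1, so the early exits need to be shown separately.
- Add a missing-not-at-random sensitivity analysis for Week 24 PEG, for example a range of shifts applied to investigator-initiated exits in each arm.

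The cost is protocol wording, a few more reminders through surveys that already exist, and a little more analysis.
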